### **10.10.1 Subject Qualification for Analysis**

All subjects for whom a signed informed consent is obtained and a CRF is started will be accounted for in the study report.

Efficacy analyses will be based on the Full Analysis Set (FAS), which is defined as all randomized subjects. Safety analyses will be based on the Safety Analysis Set, which is defined as all subjects who receive an initial study treatment and have safety data available.

---

A per protocol (PP) analysis set will be used as safety and efficacy subsets and will be defined as subjects in the FAS who complete the trial without major protocol deviations. The composition of the PP analysis set will be determined and documented in reviews of the study database. The safety and efficacy analyses based on the PP analysis set will be performed to support the results obtained for the primary and secondary safety and efficacy endpoints.

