3.1 List of Abbreviations

AE	Adverse Event
AK	Actinic Keratosis
ATC	Anatomical Therapeutic Chemical
BCC	Basal Cell Carcinoma
CCTP	Consolidated Clinical Trial Protocol
CI	Confidence Interval
CM	Concomitant Medication
DK	Denmark
FAS	Full Analysis Set
ICH	International Conference on Harmonisation
LSR	Local Skin Response
MedDRA	Medical Dictionary for Regulatory Activities
PP	Per Protocol
PT	Preferred Term
SCC	Squamous Cell Carcinoma
SD	Standard Deviation
SE	Standard Error
SMQ	Standardised MedDRA Query
SOC	System Organ Class
WHODD	WHO Drug Dictionary

4 Statistical Analysis Plan Authors

PPD [REDACTED], M.Sc., Principal Statistician, Biostata Aps, [name], tel: PPD [REDACTED], e-mail: PPD [REDACTED]

PPD [REDACTED], PhLic, Senior Clinical Project Manager, Trial Execution, LEO Pharma A/S, [name], tel: PPD [REDACTED], e-mail: PPD [REDACTED]

PPD [REDACTED]; MS, PhD (cand), Senior Medical Writer, Pharma IT, [name]; tel: PPD [REDACTED], e-mail: PPD [REDACTED]

PPD [REDACTED], MD, PhD, Associate Research Fellow, Medical Department, LEO Pharma A/S, [name], tel: PPD [REDACTED], e-mail: PPD [REDACTED]

5 Introduction

The statistical analysis will be performed as outlined in the Consolidated Clinical Trial Protocol (CCTP). This Statistical Analysis Plan contains a more technical and detailed elaboration of some points in the statistical analysis section in the CCTP.

6 Trial Analysis Sets

The full analysis set (FAS) is defined as all randomised subjects.

The safety analysis set is defined as all subjects who receive an initial study treatment and have safety data available.

The per protocol (PP) analysis set will be used as safety and efficacy subsets and is defined as subjects in the FAS who complete the trial without major protocol deviations affecting the primary and secondary safety and efficacy endpoints. Censoring as well as a full exclusion from the PP analysis set will be used in the primary analysis and in all other time-to-event analyses. A subject who is to be excluded from the PP analysis set will be in the analysis until the subject is censored at the time the event leading to exclusion from PP occurs in time-to-event analyses in case the event occurs after Day 1. This is in line with estimands defined by the composite strategy in ICH E9 (R1) addendum on estimands (1).

Please see the Analysis Set Definition Document for details.

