7.4.1 Efficacy Criteria

The efficacy criteria as defined in the CCTP are the following secondary criteria

- Complete AK clearance after the last treatment cycle (at Week 8 or 16)
- Partial (at least 75%) AK clearance after the last treatment cycle (at Week 8 or 16)
- Complete AK clearance at 12 months, defined as no AKs in the selected treatment area at any time from the last treatment cycle at Week 8 or 16 through to Month 12.

The criteria will be analysed as described in the CCTP.

Complete and partial clearance will be summarised by visit with 95% CI of clearance percentage.

Percent reduction in AK count will be summarised by visit.

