7.5.6 Changes to the Protocol

- The CCTP states: “*An interim analysis of trial data, obtained when approximately half of the trial period has elapsed, will be conducted. Assuming the time schedule shown in section 10.2, this will be prepared 3 years after study start. The interim analysis will not impact the conduct of this trial.*” This interim analysis was not conducted since the Pharmacovigilance Risk Assessment Committee at the European Medicines Agency found that the Periodic Safety Update Report was satisfactory.
- The CCTP states: “*A per protocol (PP) analysis set will be used as safety and efficacy subsets and will be defined as subjects in the FAS who complete the trial without major protocol deviations.*” Only deviations having impact on safety or efficacy will be considered. As the primary analysis is a time-to-event analysis, subjects will be censored from the PP analysis at the time of the deviation, i.e. the subject will be in the PP analysis set until the day when the deviation takes place.
- To support the primary endpoint, descriptive statistics of demographic and other baseline characteristics will be presented for the safety analysis set and not for the FAS as described in the CCTP.
- Reason for premature discontinuation from treatment is not presented as it is not captured in the eCRF. Reason for not applying trial medication according to protocol is listed.

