Table 2-51 Conversion of LSRs to MedDRA by SOC and PT: safety analysis set

LSRs

Table 2-52 – 2-57: Frequency of LSR component <component> by visit: safety analysis set

Table 2-58 – 2-63: Frequency of LSR component <component> by anatomical location and visit: safety analysis set

Table 2-64 Composite LSR score by visit: safety analysis set

Table 2-65 Composite LSR score by anatomical location and visit: safety analysis set

Table 2-66 Change in composite LSR score from baseline by visit: safety analysis set

Table 2-67 Summary of visits of maximum post baseline composite LSR score: safety analysis set

Table 2-68 Maximum post baseline LSR score by LSR component: safety analysis set

Table 2-69 Maximum post baseline composite LSR score: safety analysis set

Other safety endpoints

Table 2-70 Physical examination by visit: safety analysis set

Figures

Figure 2-1 Time to SCC: safety analysis set [[Shell 10](#)]

Figure 2-2 Time to SCC: per protocol analysis set [[Shell 10](#)]

Figure 2-3 Time to SCC or other neoplasia: safety analysis set [[Shell 10](#)]

Figure 2-4 Time to SCC or other neoplasia: per protocol analysis set [[Shell 10](#)]

Figure 2-5 Composite LSR score mean profile by visit: safety analysis set

Figure 2-6 LSR components by visit: safety analysis set

Tables and Figures, Efficacy Data (Module 4)

Tables

Table 3-1 Complete clearance by visit: full analysis set [[Shell 11](#)]

Table 3-2 Complete clearance by visit: per protocol analysis set [[Shell 11](#)]

Table 3-3 Analysis of complete clearance after the last treatment cycle: full analysis set [[Shell 12](#)]

Table 3-4 Analysis of complete clearance after the last treatment cycle: per protocol analysis set [[Shell 12](#)]

Table 3-5 Analysis of complete clearance at Month 12: full analysis set [[Shell 12](#)]

Table 3-6 Analysis of complete clearance at Month 12: per protocol analysis set [[Shell 12](#)]

Table 3-7 Partial clearance by visit: full analysis set [[Shell 11](#)]

Table 3-8 Partial clearance by visit: per protocol analysis set [[Shell 11](#)]

Table 3-9 Analysis of partial clearance after the last treatment cycle: full analysis set [[Shell 12](#)]

Table 3-10 Analysis of partial clearance after the last treatment cycle: per protocol analysis set [[Shell 12](#)]

Table 3-11 Analysis of partial clearance at Month 12: full analysis set [[Shell 12](#)]

Table 3-12 Analysis of partial clearance at Month 12: per protocol analysis set [[Shell 12](#)]

Figures

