Fitzpatrick skin type								
I	xxx	x	(xx.x)	xx	xxx	x	(xx.x)	xx
II	xxx	x	(xx.x)	xx	xxx	x	(xx.x)	xx
III	xxx	x	(xx.x)	xx	xxx	x	(xx.x)	xx
IV	xxx	x	(xx.x)	xx	xxx	x	(xx.x)	xx
History of SCC								
Yes	xxx	x	(xx.x)	xx	xxx	x	(xx.x)	xx
No	xxx	x	(xx.x)	xx	xxx	x	(xx.x)	xx

- 1) SCC: Squamous Cell Carcinoma
- 2) SCC and other neoplasia includes SCC, BCC, and in situ BCC/Bowens
- 3) N: Number of subjects in subgroup
- 4) n: Number of subjects with SCC [and other neoplasia] in subgroup
- 5) %: Percentage of subjects in the subgroup with SCC [and other neoplasia]
- 6) E: Number of events

NOTE: Subgroups might change

[figure not shown]
Shell 9: Difference in incidence of SCC [and other neoplasia] in the treatment area from baseline to Month 36: [safety/per protocol] analysis set

SCC ¹ [and other neoplasia ²]	Ingenol mebutate (n=xxx)	Imiquimod (n=xxx)
Incidence rate (%)	xx.x	xx.x
Lower 95% CI (%)	xx.x	xx.x
Upper 95% CI (%)	xx.x	xx.x
Difference		xx.x
Lower 95% CI (%)		xx.x
Upper 95% CI (%)		xx.x

- 1) SCC: Squamous Cell Carcinoma
- 2) SCC and other neoplasia include SCC, BCC, and in situ BCC/Bowens
- 3) XXX subject in xxx treatment group had two incidences of SCC [and other neoplasia]
- 4) CI: Confidence interval

Shell 10: Time to SCC: [safety/per protocol] analysis set

Shell 11: [Complete/Partial] clearance by visit: [full/ per protocol] analysis set

[Complete/Partial ¹] clearance	Ingenol mebutate (n=xxx)		Imiquimod (n=xxx)	
	N ²	(%)	N ²	(%)
Week 8				
Cleared	xxx	(xx.x)	xxx	(xx.x)
Not cleared	xxx	(xx.x)	xxx	(xx.x)
Total	xxx	(xxx.x)	xxx	(xxx.x)
Lower 95% CL ³ (Cleared)		(xx.x)		(xx.x)
Upper 95% CL ³ (Cleared)		(xx.x)		(xx.x)
Week 16⁴				
Cleared	xxx	(xx.x)	xxx	(xx.x)
Not cleared	xxx	(xx.x)	xxx	(xx.x)
Total	xxx	(xxx.x)	xxx	(xxx.x)
Lower 95% CL ³ (Cleared)		(xx.x)		(xx.x)
Upper 95% CL ³ (Cleared)		(xx.x)		(xx.x)
.				
.				
.				
Month 36				
Cleared	xxx	(xx.x)	xxx	(xx.x)
Not cleared	xxx	(xx.x)	xxx	(xx.x)
Total	xxx	(xxx.x)	xxx	(xxx.x)
Lower 95% CL ³ (Cleared)		(xx.x)		(xx.x)
Upper 95% CL ³ (Cleared)		(xx.x)		(xx.x)

- 1) Partial clearance: At least 75% reduction in AK count
- 2) N: Number of subjects
- 3) CL: Confidence limit
- 4) Only subjects with two treatment courses attend visit at Week 16

Shell 12: Analysis of [complete/partial] clearance [after the last treatment cycle/at month 12]: [full/ per protocol] analysis set

[Complete/Partial ¹] clearance	Ingenol mebutate (n=xxx)		Imiquimod (n=xxx)	
	N ²	(%)	N ²	(%)
[After last treatment cycle^{3,4}/Month 12]				

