Cleared	xxx	(xx.x)	xxx	(xx.x)
Not cleared	xxx	(xx.x)	xxx	(xx.x)
Total	xxx	(xxx.x)	xxx	(xxx.x)
Lower 95% CL ⁵ (Cleared)		(xx.x)		(xx.x)
Upper 95% CL ⁵ (Cleared)		(xx.x)		(xx.x)
Ratio of clearance rates ⁶			xx.xx	
95% CI ⁷			xx.xx to xx.xx	
p-value			x.xxx	

- 1) Partial clearance: At least 75% reduction in AK count
- 2) N: Number of subjects
- 3) Last treatment cycle is at Week 8 or Week 16
- 4) Subjects who were not clear at week 8 and by mistake not entered second treatment cycle are excluded
- 5) CL: Confidence limit
- 6) Cochran-Mantel-Haenszel estimate stratified by country, anatomical location and history of SCC
- 7) CI: Confidence interval

Signature Page for TMF-000141169 v1.0

Reason for signing: Approved	Manager Verdict(s) Name: PPD Capacity: Date of signature: 28-Aug-2019 12:29:26 GMT+0000
------------------------------	---

Reason for signing: Approved	Manager(s) Name: PPD Capacity: Date of signature: 28-Aug-2019 13:47:29 GMT+0000
------------------------------	---

Reason for signing: Approved	QC App Name: PPD Capacity: Date of signature: 30-Aug-2019 07:57:28 GMT+0000
------------------------------	---

Electronic signatures made within eTMF LEO are considered to be a legally binding equivalent of traditional handwritten signatures.

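### A table-shell footnote drops randomised subjects with an observed Week 8 result from the full-analysis-set tables of clearance after the last treatment cycle

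*SAP*

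**What the plan says.** Both documents define the analysis set in the same way. Protocol 10.10.1: "Efficacy analyses will be based on the Full Analysis Set (FAS), which is defined as all randomized subjects". SAP section 6: "The full analysis set (FAS) is defined as all randomised subjects". For the three clearance criteria, SAP 7.4.1 adds no rule of its own: "The criteria will be analysed as described in the CCTP". Protocol 10.10.4 specifies a stratified Cochran–Mantel–Haenszel comparison with a ratio of rates and a 95% confidence interval. It excludes nobody.

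The exclusion appears only in SAP Appendix II, as footnote 4 to Shell 12: "Subjects who were not clear at week 8 and by mistake not entered second treatment cycle are excluded". The marker is on the after-last-cycle option of the row heading and not on the Month 12 option. Shell 12 serves both the full and the per-protocol sets, and SAP Appendix I assigns it to these two full-analysis-set tables:

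- "Table 3-3 Analysis of complete clearance after the last treatment cycle: full analysis set"
- "Table 3-9 Analysis of partial clearance after the last treatment cycle: full analysis set"

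The by-visit display, "Shell 11: [Complete/Partial] clearance by visit: [full/ per protocol] analysis set", carries no such exclusion. SAP 7.5.6, which lists departures from the protocol, does not mention it. What that section says about deviations concerns the per-protocol set: "Only deviations having impact on safety or efficacy will be considered".

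**The concern.** The rule removes randomised subjects because of two things that happen after randomisation: a failed Week 8 outcome and a protocol deviation. A full analysis set is meant to prevent this kind of selection.

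For complete clearance the selection is one-sided, because a subject must have failed at Week 8 to be excluded. The result carries a ratio, a confidence interval and a p-value, in tables labelled as including everyone randomised.

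The exclusion also depends on a judgement. The SAP does not define a mistake, the trial is open label, and SAP 7.5.6 says that the reason for stopping treatment early was not captured in the eCRF (only the reason for not applying medication as planned is listed).

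The outputs also disagree. The same subject counts as not completely cleared at Week 8 in Table 3-1, is absent from Table 3-3, and is not excluded by any footnote from the Month 12 analysis in Table 3-5.

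**Working it through.** The plan gives no clearance rate and no number of excluded subjects, so there is no figure of its own to reproduce here. Its only sample-size figures (upper limits of 2.26% and 4.48%) concern the carcinoma rate.

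**Is the outcome observed?**

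1. The endpoint is read at Week 8 or Week 16 (protocol 10.8.1; SAP 7.4.1; Shell 12 footnote 3).
2. The Week 8 visit includes an AK count, and complete clearance means a count of zero (protocol 10.1.3, Visit 6).
3. A subject known not to be clear at Week 8 therefore has a recorded count above zero. Someone who received one cycle has Week 8 as the assessment of the last cycle received. Excluding that subject deletes data; it does not handle missing data.

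**Complete clearance.** Inputs: 240 per arm (protocol 10.3); true rate *c* and number excluded *k* are assumptions. Each excluded subject is a failure, so the numerator is fixed:

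reported rate = 240*c* / (240 − *k*)

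| Assumed rate *c* | *k* = 5 | *k* = 10 | *k* = 20 |
|---|---|---|---|
| 40% | 96/235 = 40.9% | 96/230 = 41.7% | 96/220 = 43.6% |
| 50% | 120/235 = 51.1% | 120/230 = 52.2% | 120/220 = 54.5% |
| 60% | 144/235 = 61.3% | 144/230 = 62.6% | 144/220 = 65.5% |

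**Between-arm ratio of complete clearance.** With equal true rates, the unstratified ratio (ingenol mebutate over imiquimod) is (240 − *k* for imiquimod) / (240 − *k* for ingenol mebutate):

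- 5 excluded in each arm: 235/235 = 1.00
- 10 ingenol mebutate, 5 imiquimod: 235/230 = 1.02
- 5 ingenol mebutate, 10 imiquimod: 230/235 = 0.98
- 10 ingenol mebutate, 20 imiquimod: 220/230 = 0.96

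**Partial clearance.** The criterion is a reduction of at least 75%, and subjects enter with 5 to 9 AKs (protocol 10.4.1). One remaining AK out of 5, 6, 7, 8 or 9 is a reduction of 80.0%, 83.3%, 85.7%, 87.5% or 88.9%. An excluded subject can therefore be a partial responder. At an assumed 60% rate (144/240) with 10 excluded, the reported rate lies between:

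- all 10 were partial responders: (144 − 10)/230 = 134/230 = 58.3%
- none were: 144/230 = 62.6%

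**The case against.** The strongest defence concerns the endpoint. The protocol gives every subject not clear at Week 8 a second cycle. If the last cycle means the last one required, Week 16 is the endpoint visit for these subjects, their result is missing, and excluding them fits the SAP's rule of no imputation. The wording does not rule this reading out. However, the endpoint definition and Shell 12 footnote 3 both accept Week 8, and the subject's last actual cycle was assessed then. An interest in the two-cycle result supports a per-protocol or labelled sensitivity analysis, not a reduced table under the full-analysis-set title.

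Second, SAP 7.4 allows stated exceptions to its choice of analysis sets, and the footnote is a statement in a signed SAP. That may permit another analysis. It does not make the population all randomised subjects, nor explain why SAP 7.5.6 omits the change.

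Three further points stand in part:

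- Dropout can make the denominators of Tables 3-3 and 3-5 differ anyway, so the mismatch between them is supporting evidence only.
- The footnote would print on the table, and the listings of deviations, exclusions and AK counts give some transparency. The analysis set definition document, which is not available here, may already name these subjects.
- The effect may be small. At a 50% rate, excluding 5 to 10 subjects adds 1.1 to 2.2 percentage points, against a standard error of √(0.5 × 0.5/240) = 3.2 points for one arm. The shift is nevertheless systematic and avoidable.

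**Conclusion.** The concern holds. Footnote 4 conflicts with the full-analysis-set definition in both documents and with the SAP's own deferral to the protocol, and it is not declared as a change.

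For complete clearance the direction is certain: the reported rate rises if anyone is excluded. In the scenarios shown the rise is 0.9 to 5.5 percentage points. For partial clearance the direction is open. The between-arm ratio is distorted only if the excluded fractions differ. That is possible, because only subjects not clear at Week 8 can be excluded, but nothing in the documents shows it.

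All sizes rest on assumed rates and counts; only the 240 per arm comes from the plan. Because the endpoints are secondary and the primary safety analysis is untouched, this should be fixed but does not threaten the trial's main result.

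**What to change.** 1. Delete footnote 4 from the full-analysis-set versions of Shell 12 (Tables 3-3 and 3-9).
2. State in SAP 7.4.1 that a subject without a second cycle is analysed on the observed Week 8 count, for both complete and partial clearance. This sentence would also reach subjects who had no second cycle for reasons other than a mistake, whom footnote 4 does not cover, so it should be written with them in mind.
3. Confine any exclusion for a mistakenly missed second cycle to the per-protocol tables (3-4 and 3-10), and identify the subjects in the analysis set definition document.
4. If the exclusion is kept in any table now labelled full analysis set, list it in SAP 7.5.6, report the number excluded per arm, and change the table's label.

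The cost is SAP wording and one shell footnote, with no new data. Reported complete clearance will be slightly lower wherever subjects would have been excluded.
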